**Abstract**

Title	Nivolumab in Combination with Chemoradiation for Patients with Stage II-IVB Nasopharyngeal Carcinoma, A Phase II Study with Correlative Biomarkers
Patient population	Patients with stage II-IVB endemic-type nasopharyngeal carcinoma (NPC), who are scheduled for definitive-intent chemoradiation therapy.
Rationale for Study	The current platform of chemoradiation followed by adjuvant chemotherapy is the standard means of treating NPC around the world. However, the sustained use of cisplatin-based chemotherapy throughout this treatment plan is difficult for patients to complete and the additional chemotherapy delivered in the adjuvant phase may not provide optimal efficacy against the emergence of metastasis. Immune checkpoint inhibitors have shown efficacy against multiple tumor types including nasopharyngeal carcinoma and are efficacious in combination with platinum doublets or for post-platinum disease relapse. There is a need to investigate novel approaches for the locoregionally advanced NPC population that will reduce the severe and life-altering toxicities of the current standard of care and improve the therapeutic ratio. This study has been designed to determine if nivolumab can be integrated into the current paradigm of combined chemoradiation and adjuvant chemotherapy, with improved feasibility of treatment completion over the current standard of care.
Primary Objective	To establish the feasibility of a combined chemoradiation-nivolumab regimen followed by adjuvant nivolumab. The primary endpoint will be the rate of completion of all adjuvant immunotherapy, in comparison to the rate of completion of a standard adjuvant cisplatin-based platform (historical control).
Secondary Objectives	
 
• To determine the clinical response as judged by the investigator;
 
• To determine the overall response rate at 1 year from end of treatment, as determined by RECIST 1.1 criteria;
 
• To determine the locoregional control rate at 1 year post-treatment;
 
• To determine the distant metastasis rate at 1 year post-treatment;
 
• To determine the overall survival rate at 1 year post-treatment;
 
• To determine the rate of EBV DNA clearance at end of chemoradiation and at 1 year from end of treatment;
 
• To determine the acute and late toxicity rates according to CTCAE v5.0, including immune-related adverse events (AEs);
 
• To assess patients' quality of life from baseline through 1 year from end of treatment;
 

Exploratory Objectives	
 
To determine whether PDL1-positive immunohistochemistry and novel quantitative assays correlate to clinical outcome;
 
To determine if the density of infiltrating CD3+ T cells/<math>\mu</math>m^2 correlates to clinical outcome;
 
To monitor immune changes by flow cytometry in the circulating T cell response to EBV antigens;
 
To compare the change in the circulating T-cell repertoire by TCR sequencing and single-cell T-cell profiling;
 
To quantify treatment-induced changes over time in the circulating T cell immune response to EBV using TCR sequencing and enzyme-linked immunospot (ELISPOT) assays
 

Study Design	
 
This is a phase II multi-institution, single-arm, open label clinical trial of concurrent and adjuvant nivolumab in Stage II-IVB endemic-type nasopharyngeal carcinoma patients who plan to undergo chemoradiation therapy for treatment of their cancer.
 
A run-in phase will precede expansion, to establish basic feasibility of the nivolumab schedule. The run-in cohorts will include 6 patients at each dose schedule, with 2 planned changes to the dose schedule if >33% toxicity or other dose limiting toxicity (DLT) is observed. A minimum of 6 patients and maximum of 18 patients may be enrolled in the run-in phase.
 
A total maximum of 40 evaluable patients will be enrolled for the primary endpoint. This design yields a type I error rate of 0.05 and power of 80% if the true rate of completion of adjuvant therapy is 0.7.
 
At the starting dose schedule, patients will receive nivolumab for 1 cycle prior to initiation of chemoradiation (approximately 14 days). Patients will subsequently continue with nivolumab every 14 days until completion of chemoradiation. If a dose schedule shows >33% toxicity or other DLT, then subsequently enrolled patients will be treated at the next dose schedule. In dose schedule 2, patients will start nivolumab concurrent with start of chemoradiation. In dose schedule 3, patients will start nivolumab after completion of chemoradiation (adjuvant nivolumab only). All patients will receive the same dose of nivolumab (240mg).
 
DLT criteria are grade <math>\geq</math>3 immune-related adverse events, need to hold nivolumab for >28 days due to toxicity, and for patients receiving concurrent nivolumab with chemoradiation, inability to complete chemoradiation or need to hold chemoradiation for >3 days due to immune-related toxicity.
 
Adjuvant therapy with nivolumab for 6 cycles will start at 4 weeks following completion of chemoradiation, or when immune-related toxicities are at grade 1 or lower, whichever comes later.
 
Patients will be followed for overall response rate, locoregional control and distant metastasis rates, and overall survival rate for 1 year after end of treatment.
 

Number of patients	A maximum of 40 evaluable patients will be enrolled in the study using a Simon's two-stage design for the primary endpoint. Non-evaluable patients will be replaced per the replacement policy.

Duration of Therapy	Patients will receive 23 weeks of an anticipated total therapy course, although the duration for an individual patient may be extended to as long as 33 weeks to allow for resolution of toxicities.
Duration of Follow-up	Follow-up visits will occur at 1, 3, 6, 9, and 12 months for up to 12 months after end of treatment. Survival follow-up information may be collected via telephone calls or medical records review for an additional 4 years . Survival and disease status will be collected during this 5-year period until participant death, withdrawal, or if the participant is lost to follow-up.
Duration of study	The study will reach completion in 6 years from the time the study opens to accrual.
Study Drugs	Nivolumab will be administered intravenously, at a dose of 240 mg every 14 days. Nivolumab may be held for toxicity but there are no dose reductions.
Safety Assessments	Analyses will be performed for all patients having received at least one dose of study drug. The study will use the CTCAE v5.0 for reporting of non-hematologic adverse events and modified criteria for immune related adverse events. Safety assessments will consist of monitoring and reporting adverse events (AEs) and serious adverse events (SAEs) that are considered related to nivolumab, all events of death, and any study specific issue of concern. The study period during which all AEs and SAEs must be reported begins after informed consent is obtained and study treatment is initiated and ends 12 months following the last administration of study treatment or study discontinuation/termination, whichever is earlier.
Efficacy Assessments	The primary measure of feasibility will be the rate of completion of all adjuvant therapy. This will be determined based on ability to complete all 6 cycles of adjuvant nivolumab without discontinuation for disease progression or toxicity. Secondary measures of efficacy will be clinical response as judged by the investigator; ORR by RECIST 1.1; locoregional control rate, distant metastasis rate, overall survival rate determined by standard physical examination and radiologic imaging; the rate of EBV DNA clearance at end-chemoradiation and at 1 year post-treatment as determined by PCR assay; toxicity assessments graded by CTCAE v5.0 and modified immune related criteria; and quality of life by FACT-NP, FACT-Taxane, HHIE-S, and EuroQOL EQ-5D-3L. Exploratory assessments are self-explanatory.
Unique Aspects of this Study	This is the first study to evaluate the feasibility of nivolumab integrated with cisplatin in the concurrent and adjuvant treatment of nasopharyngeal carcinoma.

## List of Abbreviations

AE	adverse event
ALP	alkaline phosphatase
ALT	alanine aminotransferase
ANC	absolute neutrophil count
AST	aspartate aminotransferase
ATC	Anatomical Therapeutic Chemical (Classification System)
AUC	area under the curve
BUN	blood urea nitrogen
CBC	complete blood cell (count)
CHR	Committee on Human Research (UCSF IRB)
CR	complete response
CRC	Clinical Research Coordinator
CRF	case report form
CSF	cerebral spinal fluid
CT	computerized tomography
CTCAE	Common Terminology Criteria for Adverse Events
CTEP	Cancer Therapy Evaluation Program
CTMS	Clinical Trial Management System
DFS	disease-free survival
DLT	dose limiting toxicity
DSMC	Data and Safety Monitoring Committee
DSMP	Data and Safety Monitoring Plan
ECOG	Eastern Cooperative Oncology Group
FCBP	female of childbearing potential
FDA	Food and Drug Administration
GCP	Good Clinical Practice
HBeAg	Hepatitis B "e" antigen
HBV	hepatitis B virus
HCT	Hematocrit
HCV	hepatitis C virus
HDFCCC	Helen Diller Family Comprehensive Cancer Center
HGB	Hemoglobin
HIV	human immunodeficiency virus
ICH	International Conference on Harmonization
IND	investigational new drug application

## List of Abbreviations

IP	investigational product
IRB	Institutional Review Board
IV	Intravenous
LDH	lactate dehydrogenase
LFT	liver function test
MedDRA	Medical Dictionary for Regulatory Activities
MRI	magnetic resonance imaging
MTD	maximum tolerated dose
NCI	National Cancer Institute
ORR	overall response rate
PD	disease progression
PK	Pharmacokinetics
PO	Per os (by mouth, orally)
PR	partial response
PRC	Protocol Review Committee (UCSF)
QOL	Quality of Life
RBC	red blood cell (count)
SD	stable disease
SD	standard deviation
SGOT	serum glutamic oxaloacetic transaminase
SGPT	serum glutamic pyruvic transaminase
ULN	upper limit of normal
WBC	white blood cell (count)

## 1 Introduction

### 1.1 Background on Indication

#### 1.1.1 Nasopharyngeal Carcinoma:

Nasopharyngeal carcinoma (NPC) is the predominant cancer type arising from the mucosal tissues of the nasopharynx. It has an incidence of 0.5-2 per 100,000 in Europe and the U.S., but it is an endemic disease in Southern China where the annual age-standardized incidence rates are as high as 20-30 cases per 100,000. NPC is also a common disease throughout the rest of Southeast Asia, the Mediterranean and the Arctic. Among NPC patients in areas dominated by the endemic type, over 95% are classified as the undifferentiated type (type 2b) according to World Health Organization criteria, while in North America, 25% are classified as keratinizing (type 1) and 12% are classified as nonkeratinizing (type 2a). The endemic-type NPC (type 2a and 2b) are near-universally associated with Epstein-Barr Virus (EBV), a strong etiologic factor that interacts with genetic predisposition and dietary intake of chemically preserved foods, while the keratinizing cancers are associated with the traditional risk factors for head and neck cancer such as alcohol and tobacco consumption.

NPC is staged according to the AJCC/UICC staging system. Presentation with stage I disease is relatively uncommon, at approximately 7% of new incidence, whereas 66% of patients present with stage II or III disease and the rest present with stage IV disease. The 5-year survival for stage I and II cancer approaches 85-90% but for non-metastatic stage III-IV disease it is around 60%.

#### 1.1.2 Concomitant Chemoradiation for Locoregionally Advanced Nasopharyngeal Carcinoma:

The current standard of care for stage I NPC is radiation monotherapy, but for newly diagnosed stage II-IVB NPC patients, treatment consists of a definitive upfront combination of approximately 7 weeks of fractionated radiation therapy (RT) with concurrent cisplatin chemotherapy that is often followed by 3 cycles of adjuvant cisplatin-5FU. This framework was established in the landmark Intergroup 0099 study, for which accrual terminated early due to a statistically significant survival advantage in the chemoradiotherapy arm as compared to radiotherapy alone.

Since that time, at least 8 randomized studies have confirmed the survival benefit of adding concurrent platinum-based chemotherapy to RT in patients with non-metastatic stage II to IVB NPC. Two meta-analyses have reported an 18% reduction in the risk of death and an absolute survival benefit of 4% to 6% at 5 years with the use of chemotherapy in addition to radiation. The largest effect was found for concomitant chemotherapy, with a pooled HR of 0.48 (95% CI, 0.32 to 0.72), which corresponds to an absolute survival benefit of 20% after 3 years, from approximately 65% to 85%.

However, despite the classic status of the Intergroup 0099 study regimen and its widespread reproduction and clinical use across the U.S. and Asia, there are numerous issues with this current standard of care, including a relatively low efficacy of this regimen of systemic chemotherapy in preventing distant metastases, difficulties with tolerability of the overall platinum burden particularly as prescribed in the concurrent plus adjuvant regimens, and a lack of recognized and efficacious alternatives to cisplatin for patients who cannot tolerate full courses of therapy.

In particular, the feasibility of adjuvant CDDP and 5-FU is problematic as only 50-60% of the patients enrolled in past trials were able to complete the prescribed regimen. For instance, in the Intergroup study, 63% of patients completed all 3 cycles of concurrent cisplatin (100 mg/m^2 given every 3 weeks) and only 55% of patients completed all 3 cycles of adjuvant chemotherapy afterwards. This is considered unfortunate as the adjuvant phase is intended to provide systemic therapy for a patient population at high risk of distant metastasis.

Justification for omission of adjuvant CDDP/5FU:

The very pressing question of whether there is any oncologic benefit to be accrued from the use of adjuvant chemotherapy in locoregionally advanced NPC was studied in a recent randomized trial from China. This phase III study compared RT with weekly CDDP followed either by 3 cycles of CDDP/5-FU or no adjuvant treatment. In 508 patients, the study found no statistically significant improvement in either progression-free or overall survival from the addition of adjuvant cytotoxic chemotherapy. Of note, in this study, 82% of patients assigned to the arm receiving weekly cisplatin plus adjuvant cisplatin-5FU started adjuvant chemotherapy, but only 63% were able to complete all 3 adjuvant cycles (52% therefore started and completed all adjuvant therapy). During adjuvant chemotherapy, 42% of patients experienced grade 3-4 toxic effects; 49% had dose reductions and 69% experienced delays in treatment. This is notable given that there was no apparent increase in rates of completion or better tolerance compared to results from the earlier era.

This Chinese randomized study specifically tested the exact additional contribution of the adjuvant phase as opposed to the Intergroup study which tested the addition of concurrent-adjuvant chemotherapy but did not examine whether the concurrent or the adjuvant phase produced the observed benefits. Therefore, many consider the Chinese study to be more relevant in speaking to the issue of whether adjuvant chemotherapy should be included in the standard of care. At this point, given the high toxicity and lack of established additional benefit of adjuvant chemotherapy, the U.S.-based National Comprehensive Cancer Network guidelines no longer consider the adjuvant phase to be supported at the highest level of evidence and have downgraded the adjuvant phase of chemotherapy to a Category 2B recommendation. The category 2B designation indicates that the evidence supporting adjuvant-phase chemotherapy is of a low grade based on historical practice and that there is not uniform consensus on the NCCN panel that it is required. In keeping with this, many major centers in the U.S. and Asia no longer consider adjuvant therapy to be necessary to the standard of care and no longer administer it. In fact, several major standard-defining nasopharynx clinical trials in Asia did not administer adjuvant chemotherapy and produced major survival benefits comparable to those that did. Lastly, from a practical standpoint, up to half of patients cannot complete adjuvant chemotherapy anyway. Thus omission of adjuvant chemotherapy is entirely within the contemporary standard of care and experimental testing of improvements to the adjuvant phase of therapy is justifiable and desperately needed.

Overall justification for study concept:

Within this context, this phase II study is designed to establish the feasibility of nivolumab integrated into the chemoradiation backbone and establish the superior tolerability and feasibility of treatment completion of this strategy as an adjuvant regimen as compared to stand of care adjuvant chemotherapy. Our study is intended to establish the role of nivolumab in the locoregionally advanced disease setting and furthermore, to provide a scientific rationale for future study based on the extent of immunomodulation achieved by nivolumab initiated as a priming

dose, given concurrently with chemoradiation and continued into the adjuvant phase. The point is that if adjuvant CDDP/5FU is being increasingly abandoned due to toxicity, adjuvant nivolumab may offer greater benefit without the excessive toxicities of traditional adjuvant cytotoxic therapy.

The study will include an initial run-in over three cohorts with planned alterations in administration of concurrent or adjuvant nivolumab if unacceptable toxicity is observed. After completion of the run-in phase, an expansion cohort will be enrolled which is designed to test formally for the feasibility of completion of adjuvant therapy as compared to the standard of care adjuvant chemotherapy.

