## 8 Statistical Considerations and Evaluation of Results

### 8.1 Study Endpoints

#### 8.1.1 Primary Endpoint:

The primary objective of this study is to establish the feasibility of completing a combined chemoradiation-nivolumab regimen followed by adjuvant nivolumab. Feasibility of completing adjuvant phase therapy is a key relevant clinical question in ongoing NPC research, as the efficacy of the current standard of care of platinum-based concurrent and adjuvant phase chemotherapy is in question but its toxic effects are severe, resulting in frequent early discontinuation of adjuvant therapy. Adjuvant nivolumab is likely to be much more tolerable and feasible and if feasibility of the program is established, this will open the possibility of testing its efficacy in various subsets of patients.

**Feasibility of treatment completion:** The primary endpoint of the study will be the rate of completion of all adjuvant immunotherapy, in comparison to the rate of completion of a standard adjuvant cisplatin-based platform. The rate of completion of all adjuvant therapy by patients treated at the MTD schedule will be determined and compared to a historical control rate of 52%.

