## 8.2 Determination of Sample Size and Accrual Rate

### 8.2.1 Sample Size and Power Estimate

We expect the true completion rate of this combined chemoradiation-nivolumab regimen followed by adjuvant nivolumab to be 70%, versus the null hypothesis of 50% (the rate of completion of a standard adjuvant cisplatin-based platform is 52%).

Simon's two-stage design will be used to test this endpoint. In the first stage, 22 patients will be accrued. If 11 or fewer completions, the study will be stopped. Otherwise, 18 additional patients will be accrued for a total of 40 participants.. The null hypothesis will be rejected if 26 or more completions are observed in 40 patients. This design yields a type I error rate of 0.05 and power of 80% when the true completion rate is 0.7.

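### The 52% historical control multiplies 82% by 63% without stating the denominator of the 63%; the control could be 52% or 63%, and success at 26/40 does not by itself show superiority over either

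*Combined protocol and SAP*

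**What the plan says.** Section 1.1.2, in the part justifying omission of adjuvant chemotherapy, takes three figures from the randomised trial in China. The first is that 82% of those allocated to the adjuvant arm began that phase. The other two come together: "but only 63% were able to complete all 3 adjuvant cycles (52% therefore started and completed all adjuvant therapy". Only the 82% carries a stated denominator, the patients assigned to the arm. For the Intergroup study the same section reports that "only 55% of patients completed all 3 cycles of adjuvant chemotherapy afterwards".

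The 52% then becomes the benchmark for the primary endpoint. Section 8.1.1 says the completion rate will be "determined and compared to a historical control rate of 52" (per cent), and section 8.2.3 repeats this. Section 8.2.1 sets the null at 50% and the target at 70%, noting in parentheses that "the rate of completion of a standard adjuvant cisplatin-based platform is 52" (per cent).

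The plan contains two decision rules:

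- Section 8.2.1: stop if 11 or fewer of 22 complete; otherwise declare success at 26 or more of 40. Stated type I error 0.05, power 80%.
- Section 8.2.4: stop if 7 or fewer of 15 complete; otherwise declare success at 18 or more of 28. Stated type I error 0.09, power 80%.

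The overall justification in section 1.1.2 says the study is meant to establish that completion is superior to that of adjuvant chemotherapy.

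**The concern.** Multiplying 82% by 63% is right if 63% of those who started went on to finish. It is wrong if 63% of those assigned finished: every completer is also a starter, so the product would count the non-starters twice, and the completion rate would simply be 63%. The sentence does not say which base applies.

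This matters because the 52% is the only comparator named for the primary endpoint and the only support offered for a 50% null. The protocol's claim is about superiority to adjuvant chemotherapy, so what counts is how often the success rule is met when nivolumab completion merely equals the control. That probability depends heavily on whether the control is 52% or 63%.

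**Working it through.** **Inputs.** 82%, 63% and 52% from section 1.1.2; null 50%, target 70% and the 22/40 rule from section 8.2.1; the 15/28 rule from section 8.2.4.

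**Step 1: reproduce the control.** 0.82 × 0.63 = 0.5166, which rounds to 52%. The plan's figure reproduces, on the assumption that 63% is of starters. If 63% is of assigned patients, no multiplication applies and the control is 63%.

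**Step 2: reproduce the design.** With true completion rate p, the exact probability of declaring success is

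- 22/40 rule: sum over x = 12 to 22 of P(X = x) × P(Y ≥ 26 − x), with X ~ Bin(22, p) and Y ~ Bin(18, p);
- 15/28 rule: sum over x = 8 to 15 of P(X = x) × P(Y ≥ 18 − x), with X ~ Bin(15, p) and Y ~ Bin(13, p).

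At p = 0.50 and 0.70 this gives 0.040 and 0.803 for the 22/40 rule, and 0.090 and 0.801 for the 15/28 rule. Both agree with the plan: 0.040 is within the stated 0.05, and the shortfall comes from the discreteness of the binomial.

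**Step 3: evaluate at the possible controls.**

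| True completion rate | 22/40 rule | 15/28 rule |
|---|---|---|
| 50% (null) | 0.040 | 0.090 |
| 52% (63% is of starters) | 0.066 | 0.129 |
| 63% (63% is of assigned) | 0.46 | 0.52 |
| 70% (target) | 0.803 | 0.801 |

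Using the unrounded 0.5166 in place of 52% gives 0.061 and 0.122, so rounding does not change the picture.

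**Step 4: what a bare success would show.** 26/40 = 65%. The exact (Clopper-Pearson) two-sided 95% interval is 48.3% to 79.4%, which contains both 52% and 63%. The one-sided 95% lower bound is 50.8%, above 50% but below 52%.

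**For scale only.** Keeping 40 patients and the same first stage, an error of at most 0.05 would need 27/40 against 52% (error 0.034, power 0.70 at a true rate of 70%) and 31/40 against 63% (error 0.038, power 0.20). The plan adopts neither as its null.

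**The case against.** The strongest reply is that the authors' meaning is clear enough. The word linking 63% to 52% is an inference, and the result is described as starting and completing, so they took 63% as conditional on starting. The surrounding text in section 1.1.2 fits 52% better. Completion among enrollees in past trials is put at 50–60%, and 63% would lie outside that. The Intergroup figure is 55%, and completion in the newer trial is described as no better than before. As many as one patient in two is said not to finish, which matches 48% non-completion better than 37%. All of this stands as evidence of what the authors intended. It does not verify the source, and the last two statements may themselves rest on the 52%.

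Three stronger readings are tempting and should not be drawn:

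- A reader might infer that the sentence gives both 82% and 63% as shares of assigned patients. It attaches that base only to the 82%.
- A reader might infer that the Intergroup benchmark was built from the same construction and left unmultiplied, so that consistency requires 63% here. The two Intergroup figures (63% and 55%) describe different phases, concurrent cisplatin and adjuvant chemotherapy. The newer trial's figures describe starting and finishing one phase. The comparison says nothing about the missing denominator.
- A reader might infer that 26/40 would show no improvement if the control is 63%. 65% lies above 63%; the supportable statement is that it is not distinguishable from 63%.

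It is also fair to say that the formal test is against 50%, and that its error and power are correct whichever way the 63% is read. The difficulty is the step from rejecting 50% to claiming superiority over a control that the plan itself puts at 52%.

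**Conclusion.** The multiplication is correct as arithmetic, but its premise is unstated and cannot be confirmed from the documents. The control is 52% if the 63% refers to starters, which is the better-supported reading, and 63% if it refers to all assigned patients.

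For a regimen no better than the control, the chance of declaring success under the 22/40 rule is 0.066 at 52% and 0.46 at 63%; under the 15/28 rule it is 0.13 and 0.52. The 0.46 and 0.52 hold only on the less supported reading. The 0.066 needs no assumption beyond the plan's own 52%: it exceeds the stated 0.05 because the null is set two points below the named control. So on either reading, just meeting the threshold rejects a completion rate of 50% and does not by itself establish superiority to adjuvant chemotherapy.

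These probabilities treat the control as a known constant and completions as independent with a common rate. The figure should be verified before the primary result is interpreted.

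**What to change.** 1. Take the number of completers and the number assigned from the cited trial report, and use completers divided by assigned as the control in sections 1.1.2, 8.1.1, 8.2.1 and 8.2.3.
2. If the 63% is of starters, say so in section 1.1.2 (63% of the 82% who started) and keep 52%. If it is of assigned patients, delete the product and replace 52% by 63% in all four sections.
3. In either case, state in section 8 that reaching 26/40 rejects a completion rate of 50% and does not by itself establish superiority to adjuvant chemotherapy. Align the superiority wording in section 1.1.2 with this.
4. Report the exact 95% confidence interval of the observed completion rate beside the verified control.

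The cost is one look-up in a reference already cited and some rewording; no extra patients are needed. The downside is a weaker claim and, if the 63% proves to be of assigned patients, a less favourable comparator.
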